
## Effect of a Digital Engagement Strategy on Healthcare Worker Mental Health and Well-being: A Randomized Controlled Trial

Way to Health. Participants will not be informed as to why they were selected, and confidentiality will be maintained.

### *7.5 Subject Compensation*

To promote retention, participants will be emailed up to 4 times and texted (up to three times) to nudge survey and assessment completion. For compensation, each participant will receive up to \$200: \$50 at enrollment, \$75 at 6 months and \$75 at 9 months for 3 total surveys. Submission for subject reimbursement will occur immediately upon completion of surveys and assessments and occur through the Way to Health platform which facilitates timely payment. Each participant will receive \$50 for interview completion.

## **8. Study Procedures**

### *8.1 Consent Process*

To recruit potential study participants, we will send an email about the study to the entire Penn Medicine employee listserv, these individuals are the same recipients of Penn Medicine news and COVID-19 updates who have received prior information about the availability of Cobalt. Emails will be sent up to 4 times to this employee list. This proposal includes a letter of support from the Penn Medicine Director of Human Resources and Penn Medicine Chief Operation Officer indicating support for the project and access to these listservs. Participants will provide electronic informed consent before participation in the study. The electronic consent form is hosted on Way to Health, HIPAA Compliant Platform. Participants will be notified that enrollment is voluntary and declining to participate will not change their access to Cobalt or have an impact on their employment. Participants will be consented with ample time to discuss consent. Participants will be given contact information (including telephone and email) for the principal investigator ([name]), and the University of Pennsylvania IRB to address any potential concerns. A detailed Manual of Operations will be developed for the study and procedures will be designed to ensure efficient and prompt updating. Our project is designed to function entirely remotely (recruitment, consent, enrollment, survey completion) All study participants read and review the informed consent document independently on Way to Health but research team members are readily available to discuss the form and answer questions via email or telephone communications, all noted on the instructions of the informed consent document on Way to Health. All investigators have experience in developing a manual of operations. All study staff will undergo a thorough training and certification procedure prior to protocol implementation, including CITI Course in the Protection of Human Research Participants online training in research ethics. The initial training will be conducted by the PI and will include an overview of the study, detailed explanation of the study protocol, and hands-on practice of specific protocol components. All study staff will be observed conducting randomly selected protocol duties at least twice annually and evaluated using specifically designed checklists.

#### *8.1.1.1 Waiver or Alteration of Informed Consent*

Not applicable

#### *8.1.1.2 Minimal Risk*

Since we are recruiting Penn Medicine employees, the informed consent highlights how their Penn Medicine employer, director, supervisor, or co-worker may be an investigator in this research study. The document also includes language on how if the individual chooses not to participate, there will be no loss of benefits to which they are otherwise entitled. Their employment is not in jeopardy based on their enrollment status. Given that the study compares the same process delivered as either a pull (usual care = Cobalt) or a push (intervention = Cobalt +) we believe risk is low. Nevertheless, we will engage a 3-member independent Data and Safety Monitoring Board to oversee the trial. In accordance with conventional practices, we will not identify members in advance so as not to disqualify potential proposal reviewers. All subjects will be consented for participation and will have the ability to withdraw at any time. There is minimal risk to the participants as Penn Cobalt will triage patients accordingly to level of services for mental health support. All qualitative results will be de-identified and any collected

## Effect of a Digital Engagement Strategy on Healthcare Worker Mental Health and Well-being: A Randomized Controlled Trial

PHI data will be stored securely and separately. Participants can elect to not participate in the study without any consequences. Participants can also opt-out of participating at any time. All employees have access to Cobalt and associated services; participants in the intervention arm may be less likely to experience risks associated with the research because they are receiving pushed services designed to reduce barriers to access of mental health services.

### *8.1.1.3 Impact on Subject Rights and Welfare*

We will be obtaining informed consent from patients who have been provided a thorough explanation of the study and the opportunity to ask any questions about study participation. Patients will be read the entire consent and given the option to participate.

### *8.1.1.4 Waiver Essential to Research*

All participants will be recruited through remote procedures.

### *8.1.1.5 Written Statement of Research*

This study does not operate under a written statement of research.

### *8.2 Procedures*

We will conduct a prospective two-armed randomized control trial to test the effect of tailored mental health support on self-reported HCW mental health (anxiety and depression) during the response and recovery phases of the COVID-19 pandemic. The control group will have access to Cobalt which is usual care for all Penn Medicine employees. The Cobalt platform is web-based and is accessible from any device or desktop. Cobalt uses contextual surveys and evidence-based assessments to triage individual users to curated content and appropriate group or individual support. The current, and usual care, model is a digital version of what exists at other institutions where resources are available for staff to access wellness and mental health services. The usual care Cobalt model requires staff to personally initiate multiple steps: 1) identify a personal need for support, 2) know where to seek support and care, 3) schedule an appointment, and 4) attend the appointment. In this context, the individual has to pull the resources they need and there may be several barriers to completing each step. This is particularly relevant as mental health conditions can compromise insight, motivation, and decision making, thereby making self-directed engagement in care (pull) more challenging. The RCT will compare this pull model with a new model, the intervention named Cobalt+, which will proactively reach out to and engage individuals in order to reduce barriers in identifying a need for and accessing mental health care. The intervention group will have access to the same Cobalt resources as those in the usual care group but will also receive a comprehensive suite of services including: 1) monthly automated text messaging reminders and links to Cobalt resources 2) intermittent mental health assessments (PHQ-9, GAD-7) at enrollment, month 2, month 4 and month 6 which triage individuals to an opt-out appointment with a resilience coach, psychotherapist, or psychiatrist based on their results. Of note, all employees will have access to Cobalt whether they are in the study or not. Through the proposed RCT we will evaluate whether the intervention, a proactive model of care delivery (Cobalt+) impacts the primary outcome measure (depression and anxiety) and secondary outcome measures (well-being, satisfaction with access to care, and measures of work productivity [e.g. absenteeism]). Difficulties due to health conditions mental health domains will be assessed at the month 9 follow up survey.

### **9. Analysis Plan**

We will conduct an intent to treat (ITT) analysis. The ITT analysis will include all randomized participants in the groups to which they were randomly assigned. Baseline demographic and clinical characteristics will be reported as frequency and percent for categorical variables and median and distribution for continuous variables. We will compare baseline characteristics between intervention and control arms using t-tests for continuous variables and chi-squared tests for categorical variables. The goal of these comparisons will be to determine if the two arms are balanced on baseline variables after randomization. Our primary analysis will focus on the difference in PHQ-9 and GAD-7 scores at 6 months between the two arms. We will estimate and test differences in means between arms using two- sample

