#### 7.2 Subjects at Penn 1,275

#### 7.3 Accrual

To recruit potential study participants, we will send an email about the study to the entire Penn Medicine employee listserv, as these individuals are the same recipients of Penn Medicine news and Covid-19 updates who have received prior information about the availability of Cobalt. Emails will be sent up to 5 times to this employee list. The plan to outreach to employees in this manner has been approved by both Penn Medicine Human Resources and the Penn Medicine Chief Operation Officer. We will specifically engage recruitment champions in the study design and for support in extending the reach of the recruitment email to underrepresented minority HCWs. These recruitment champions will include each Departments Vice Chair for Diversity and Inclusion to support sending the email about the study to their Departments and groups within their Departments specifically focused on diversity and inclusion. We will also engage Centers, Departments, and Groups at Penn Medicine to support dissemination of the study announcement. These include the Office of Inclusion and Diversity, the Alliance of Minority Physicians, Penn Medicine Center for Health Equity Advancement, Bold Solutions Initiative, FOCUS on health and leadership for women, Penn Promotes research on sex and gender in health, and the Program for Health Equity in Education and Research. Furthermore, we will recruit in-person across the Penn Medicine campus such as tabling outside of prominent buildings and departments (New Pavilion and cafeterias) and attend department morning huddles / meetings to accommodate staff members who have limited access to their email accounts. We will also be intentional about diversity of representation in the images in all study materials and highlight the diversity in our project team. We base our power considerations on baseline data presented in an RCT conducted by Graham et al. In their study, they report a mean baseline PHQ-9 of 14.0 (SE=5.0) and mean GAD-7 of 11.6 (SE=4.6). We assume a type I error rate of 2.5% (.05/2) to account for the two

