## Effect of a Digital Engagement Strategy on Healthcare Worker Mental Health and Well-being: A Randomized Controlled Trial

separate outcomes that we will be evaluating. We aim to enroll 1275 participants with the anticipation that there will be 27.5% attrition.

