## Effect of a Digital Engagement Strategy on Healthcare Worker Mental Health and Well-being: A Randomized Controlled Trial

t-tests and generalized linear models that account for baseline measurements of PHQ-9 and GAD-7. Missing data will be assessed for patterns and multiple imputation will be used if deemed appropriate. Baseline covariates that are found to be imbalanced between arms may be adjusted for in the model if they were deemed to be potential confounders a priori to adjust for potential confounding and for efficiency gain. We will use all available PHQ-9 and GAD-7 scores on eligible patients from randomization through the last observation. A p<0.05 will be deemed statistically significant but emphasis will be placed on point estimates and confidence intervals. Secondary outcomes of mental healthcare utilization, satisfaction with connection to services, and qualitative feedback on mobile engagement will also be modeled using GEE with mean models specified based on the distribution of the specific outcome (e.g. Poisson or negative binomial for number of mental healthcare visits, logit for binary responses). Potential associations between system-level or regional level case burden and PHQ-9 and GAD-7 scores at baseline and over-time will be assessed with generalized linear models and GEE. Exploratory Aim 1: Statistical approach: The statistical approach for studying HTE will be to test for the statistical interaction between the intervention and race and separately by gender in the GEE models described above. Although our study was not designed specifically to detect HTE, if 20% of our trial participants are Black (based on targeted recruitment efforts), our study will achieve 80% power (assuming type I error of 0.05) to detect a 1.8 difference in mean GAD-7 scores and a 2.0 difference in mean PHQ-9 scores between arms at 6 months. We anticipate that at least 50% of participants will be female. Hence, our study is powered to detect a 1.2 difference in mean GAD-7 scores and a 1.3 difference in mean PHQ-9 scores between arms at 6 months among women. Aim 2: Power: no power calculation will be performed for this qualitative aim consistent with prior qualitative aims we will aim to interview 80 participants from Aim 1 and evaluate themes until saturation Analysis: Using thematic analysis, we will analyze HCW interview transcripts to identify recurring themes in attitudes and beliefs toward mental health, well-being, and mental health care or resources. Interview audio will be transcribed and uploaded into Nvivo software (available as a Penn resource). In total we plan for up to 80 semi-structured interviews, or until inductive thematic saturation is reached in each group meaning no new themes are emerging. Analysis of qualitative, semi-structured interviews utilizes a series of systematic steps in transcribing, developing a code for thematic content, and subsequent coding of interviews. A modified grounded theory approach will be used to evaluate interview transcriptions. Analysis will begin shortly after the first few interviews are completed. An emergent, iterative open coding process will be followed and two trained coders from the research team will jointly read five transcripts and draft the outline of a codebook. Each coder will then independently code five more transcripts and adjust the codebook as needed. We will review the codes, resolve discrepancies and finalize coding procedures. Following adjudication of any areas of discrepancy, the research team coders will be assigned batches of transcripts for independent coding, sharing 25% of the transcripts in each batch for ongoing inter-rater agreement assessment. We will review coding for interrater reliability, measured by Cohens kappa (0.8), and overall comprehensiveness. If a high kappa is not achieved, further double coding and refining of the code will continue. This approach to coding and analyzing qualitative data has been widely used. Strategies used to ensure reliability and validity in the qualitative data will include a comprehensive audit trail, checks between coders, team debriefing, and corroboration of findings across participants.

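### Section 9 promises an ITT analysis of everyone randomized, but both named primary methods use only people with a 6-month score, imputation is optional, and neither method is named as governing

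*Combined protocol and SAP*

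**What the plan says.** All references are to the final protocol.

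- **Population (section 9).** "The ITT analysis will include all randomized participants in the groups to which they were randomly assigned".
- **Primary comparison (section 9).** "Our primary analysis will focus on the difference in PHQ-9 and GAD-7 scores at 6 months between the two arms". The tests are two-sample "t-tests and generalized linear models that account for baseline measurements of PHQ-9 and GAD-7". The two are listed side by side, and neither is named as the one that decides.
- **Missing scores (section 9).** "Missing data will be assessed for patterns and multiple imputation will be used if deemed appropriate". No criterion, decision-maker, imputation model or missing-data assumption is given.
- **Data used (section 9).** "We will use all available PHQ-9 and GAD-7 scores on eligible patients from randomization through the last observation".
- **Expected loss (section 7.3).** "We aim to enroll 1275 participants with the anticipation that there will be 27.5% attrition". The time point of the attrition is not stated.
- **GEE (section 9).** Secondary outcomes "will also be modeled using GEE with mean models specified based on the distribution of the specific outcome". GEE is also named for the case-burden associations and for the race and gender interactions. It is not named for the primary 6-month comparison.

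No section says how a randomized person without a 6-month score enters the primary result.

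**The concern.** Inclusion of everyone randomized is stated as a property of the analysis, but the named methods do not have it. A t-test or a single-visit regression on the 6-month score drops anyone whose score is missing. Deciding on imputation after inspecting missingness patterns does not repair this: the choice would be made with the data in view, and observed patterns cannot show that completers represent the rest.

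The protocol's own reasoning makes selective loss plausible. Section 8.2 says that mental health conditions can weaken motivation and make self-directed engagement harder. Only the Cobalt+ arm is described as receiving monthly prompts, assessments at months 2 and 4, and opt-out appointments. If symptoms drive dropout differently in the two arms, the completers are no longer comparable groups, and a completer analysis would be reported as ITT.

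**Working it through.** **1. How many could be left out.** From section 7.3, N = 1,275 and attrition is 27.5%.
1,275 × 0.275 = 350.6, about 351. 1,275 × 0.725 = 924.4 remain, or 462.2 per arm (1:1 allocation assumed, as the ratio is not stated).

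**2. The plan's own power figures.** Section 9 gives power only for subgroups. The minimum detectable difference (MDD) is (1.960 + 0.842) × SD × √(2/n per arm), for 80% power at two-sided 0.05. SD is 4.6 for GAD-7 and 5.0 for PHQ-9; section 7.3 prints these as standard errors, and I read them as standard deviations.

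| Subgroup | Stated GAD-7 / PHQ-9 | MDD, 924 completers | MDD, all 1,275 | MDD, 1,000 completers |
|---|---|---|---|---|
| Women (50%) | 1.2 / 1.3 | 1.20 / 1.30 | 1.02 / 1.11 | 1.15 / 1.25 |
| Black participants (20%) | 1.8 / 2.0 | 1.90 / 2.06 | 1.61 / 1.75 | 1.82 / 1.98 |

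The figures for women reproduce on 924 completers. Those for Black participants reproduce only on the 1,000 completers implied by the initial protocol (1,250 with 20% attrition). Neither set fits all 1,275, where power would be 88 to 91%. The design was sized on people with data.

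**3. Bias of the unadjusted t-test on completers (PHQ-9).** Suppose that in one arm only, dropouts have a baseline mean above completers by a given gap in SD units. Then:
bias = 0.275 × gap × 5.0 × baseline-to-6-month correlation.
Standard error = 5.0 × √(2/462.2) = 0.329.
Overall MDD at 80% power and two-sided 0.025 = (2.241 + 0.842) × 0.329 = 1.01.
False-positive rate = P(|Z + bias/0.329| > 2.241).

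The gap and the correlation are assumptions; the documents give neither.

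| Gap | Correlation | Bias (points) | False-positive rate |
|---|---|---|---|
| 0.5 SD | 0.5 | 0.34 | 12% |
| 0.5 SD | 0.6 | 0.41 | 16% |
| 0.5 SD | 0.7 | 0.48 | 22% |
| 0.25 SD | 0.5 to 0.7 | 0.17 to 0.24 | 5 to 7% |

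**4. The same dropout under the other planned method.** Simulations used 637 per arm, no true effect, selective dropout in one arm with a gap of about 0.5 SD, and rejection at the 2.5% level. Each cell shows absolute bias and rejection rate.

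| What drives dropout | t-test | Baseline-adjusted model, completers | Multiple imputation |
|---|---|---|---|
| Baseline PHQ-9 only (1,500 trials) | 0.44, 17% | 0.01, 1.8% | not run |
| Two baseline scales (1,500 trials) | 0.45, 20% | 0.08, 3.1% | 0.00, 2.3% |
| Two baseline scales (800 trials) | 0.48, 23% | 0.08, 2.6% | 0.01, 2.6% |

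A further check of the two-scale case put the adjusted model's bias at about 0.1 points. In the two-scale runs the standard error was the same for the adjusted model and for imputation (0.27 in one, 0.26 in the other). Simulation error on a 2.5% rate is √(0.025 × 0.975/1,500) = 0.4 percentage points (0.6 with 800 trials). The rejection rates for the adjusted model and for imputation are therefore all within two simulation standard errors of nominal.

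**The case against.** The strongest reply is that the plan already contains the remedy for most of the bias. When dropout depends on baseline PHQ-9, the baseline-adjusted model on completers is nearly unbiased without imputation. When a second scale also matters, the residual is about 0.08 to 0.1 points, roughly 8 to 10% of the 1.01-point MDD. **This stands.** The large t-test figures measure the cost of leaving the t-test eligible as the primary test, not the cost of omitting imputation.

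Other points on that side:

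- *The 351 is not the protocol's month-6 figure.* Correct. Surveys run to month 9 and the attrition is undated.
- *Imputation is mentioned.* Correct, so people can drop out of the result; one cannot say that they will. But an option does not meet a promise to include everyone.
- *The sentence on using all available scores may point to a repeated-measures analysis.* It is ambiguous. Scores at months 2 and 4 are described only for Cobalt+, so such a model would retain people unevenly by arm. Nor does the sentence say that last scores are carried forward.
- *One-arm selective dropout is assumed.* It is. The payments of $75 at 6 and 9 months, and the reminders of up to 4 emails and 3 texts (sections 7.4 and 7.5), are described without distinction by arm and may limit it.
- *GEE tolerates missingness that depends on covariates in its mean model.* True, and GEE plays no named part in the primary comparison.

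**Conclusion.** The gap is real but moderate. Section 9 claims that everyone randomized is included, and its named primary methods do not deliver this for anyone without a 6-month score. About 351 of 1,275 are exposed if the 27.5% applies at month 6. Under the assumed one-arm dropout with a 0.5 SD gap, bias is 0.34 to 0.48 points (false-positive rate 12 to 22%) if the t-test governs, and about 0 to 0.1 points (rejection about 2 to 3%) if the adjusted model governs. The results also assume 1:1 allocation, SDs of 5.0 and 4.6, and the 2.5% level of section 7.3, although section 9 uses 0.05.

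A reader might infer three stronger conclusions that the documents do not support:

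- *The primary result carries a bias of some 40% of the detectable difference.* That ratio (0.41/1.01) belongs to the unadjusted t-test alone.
- *The sponsor has committed to a completer analysis, because the power figures fit completers.* Enlarging a sample for expected attrition is ordinary practice and settles nothing about the analysis set.
- *GEE removes people from the primary result.* It is named only for other analyses.

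**What to change.** In section 9:

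1. Name the baseline-adjusted model as the primary estimator for each scale, and drop the unadjusted t-test as a primary test.
2. Replace "Missing data will be assessed for patterns and multiple imputation will be used if deemed appropriate" with a commitment to multiply impute missing 6-month PHQ-9 and GAD-7 for all randomized participants, separately by arm. Predictors: baseline PHQ-9 and GAD-7, other scales measured at enrollment, demographics, any month-9 scores and, in Cobalt+, the month-2 and month-4 scores. Analyse the imputed sets with the model in step 1.
3. Report the observed-data analysis as supportive, and do not call it ITT.
4. Use the same imputed sets for the PHQ-9 and GAD-7 race and gender interaction models. These sets contain no imputed satisfaction or utilization data, so the other secondary outcomes need their own imputation or should be labelled available-case.
5. State in section 7.3 the time point to which the 27.5% refers.

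The cost is plan wording and some programming, with no new data. In the simulations the standard error did not rise. The downside is that the primary result then rests on a stated imputation model that assumes data are missing at random.
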